9.3.4 Removal of Subjects from Treatment or Assessment

Withdrawn subjects are those who do not complete all evaluations and procedures outlined in the protocol. Subjects who discontinue taking study drug for any reason must also be withdrawn from the study. All adverse events that are present when the subject withdraws from the study will be followed as described in [Section 9.6.2.1](#).

Subjects must be withdrawn from the study for any of the following events:

- Elevated AST or ALT 3 times upper limit of normal (ULN) or greater and elevated bilirubin greater than 2 times ULN and no other explanation of these abnormal tests
- An SAE assessed as related to study treatment by the Investigator or Medical Monitor
- Clinically significant worsening of acne status requiring change of treatment in acne management (eg. increased size or number of nodules)

Subjects may be withdrawn from the study for one of the following events:

- Adverse Event: An AE that, in the opinion of the Investigator or Sponsor, suggests that continued participation in the study is not in the subject's best interest for safety reasons. Only a primary AE leading to withdrawal should be noted to be the reason for withdrawal.
- Abnormal Laboratory Result: Any clinically significant laboratory abnormality that requires withdrawal of the subject from the study should be considered an AE leading to withdrawal. If possible, laboratory tests will be repeated for any results that were clinically significantly abnormal until the abnormality is resolved or stabilized to the satisfaction of the Investigator in consultation with the Medical Monitor.
- Lost to Follow-up: Confirmed at minimum by 2 phone calls and a traceable letter without answer.
- Subject Request: Subject requests for any reason to be withdrawn or withdraws his/her consent.
- Protocol Deviation: A subject may be withdrawn from the study at the discretion of the Investigator or Sponsor due to poor compliance with protocol requirements that may compromise the study results or subject safety.
- Other: Other reasons include but are not limited to: Investigator decision that it is in the subject's best interest to be withdrawn, administrative reasons, relocation of subject, etc. If a subject becomes pregnant during the study, the subject will be withdrawn from the study and followed through to the conclusion of the pregnancy.

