9.5.2.5 Visit 4 (Week 12 ± 3 days)

- Perform physical examination, including weight
- Measure blood pressure and heart rate
- Perform 12-lead ECG
- Collect blood and urine samples for clinical laboratory tests hematology, serum chemistry, urinalysis, and lipids ([Appendix 2](#))
- Obtain blood sample for thyroid function evaluation ([Appendix 2](#))
- Perform urine pregnancy test – females of childbearing potential only
- Perform the IGA for face
- Perform facial lesion count of inflammatory and noninflammatory lesions
- Obtain facial photographs
- Perform IGA for the neck, chest, and back

- Record concomitant medications
- Administer Skindex questionnaire
- Adverse event query
- Review and collect completed subject diary pages
- For subjects participating in PK sampling, collect blood samples as directed in Section 9.6.3.4 for Visit 4/Week 12 for PK Schedule 1, PK Schedule 2, **and PK Schedule 3**
- Collect previously dispensed study drug and perform study drug accountability and assess study drug compliance
- Record date of last study drug dose **and the dose taken in clinic at the Visit 4/Week 12**
- **For subjects participating in PK Schedule 3, schedule the next study visit at Visit 5/Week 13 ± 3 days**
- Complete Study Termination Form **(unless subject is participating in PK Schedule 3)**

9.5.2.6 Visit 5 (Week 13 ± 3 days) (for subjects participating in PK Schedule 3)

- **Perform physical examination, including weight**
- **Measure blood pressure and heart rate**
- **Perform urine pregnancy test – females of childbearing potential only**
- **Record concomitant medications**
- **Adverse event query**
- **Complete Study Termination Form**

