11.5.6 Sensitivity Analyses

Sensitivity analyses will investigate the impact of missing data on the robustness of the results. Reasons for missing data and time to drop-out will be explored in a descriptive fashion for each treatment. Efficacy responses through time for each treatment will be investigated for each treatment for subjects that completed the study versus for those subjects that discontinued the study. Additionally, logistic regression models may be used to explore efficacy responses for subjects who completed the study compared to those subjects who dropped out. Finally, the following sensitivity analyses of the co-primary efficacy endpoint data will be provided to explore the impact of missing data on the robustness of the results. Additional sensitivity analyses may be described in the Statistical Analysis Plan prior to database lock.

Sensitivity Analyses for Continuous Variables

- Efficacy data will be summarized and analyzed **according to an ANCOVA model with the baseline value as a covariate and effects of treatment and (pooled) site** using the **per-protocol (PP) population with OC data**.
- **LOCF will be used as an imputation method for cases where the Week 12 CFB in inflammatory lesion counts value is missing. The endpoint will then be analyzed according to an ANCOVA model with the baseline value as a covariate and effects of treatment and (pooled) site.**
- Baseline observation carried forward will be used as an imputation method for cases where the Week 12 CFB in inflammatory lesion counts value is missing. The endpoint will then be analyzed according to the **ANCOVA model with the baseline value as a covariate and effects of treatment and (pooled) site**.
- Mixed model repeated measures (MMRM) analysis will be used to explore the sensitivity of data handling for CFB in inflammatory lesion counts for subjects who withdraw from the study. The model will include the fixed effects of treatment, pooled site, and visit, the baseline value as the covariate, and the treatment-by-visit interaction term. An unstructured covariance matrix will be used initially in the model for the correlation pattern among the repeated measures. If this does not converge, then the Toeplitz covariance structure (TYPE=TOEP in SAS MIXED procedure) will be used instead. If the results from the MMRM analyses differ qualitatively with the results from the

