1. Did not meet inclusion/exclusion criteria
2. Have taken any interfering concomitant medications
3. Duration of treatment less than 68 days, or did not complete study based on subject exit status, or overall study drug compliance less than 80%
4. Received treatment different from the assigned treatment

A list of subjects with conditions 1, 2, and 3 above prior to unblinding will be created. This list will be reviewed by a Clinical Representative to determine which subjects are to be excluded from the PP population. These subjects will then be documented in a signed memo prior to unblinding. The subjects who received treatment different from the assigned treatment (condition 4) will be identified after unblinding and will be documented in a separate signed memo.

Three “visit types” will be defined for the purposes of analysis and summaries:

- Observed Cases (OC) – includes assessments collected at each scheduled visit. All applicable efficacy and safety variables will be summarized for OC visits.

- Multiple Imputation Data – for the primary and secondary efficacy endpoints, missing data will be imputed using multiple imputation procedures further described in Section 16.2.
- LOCF – defined as the last post-baseline data recorded for each efficacy variable. This visit will be denoted as Week 12 (LOCF) and will only be used to summarize efficacy data. The LOCF visit provides missing value imputation for subjects who do not provide data for the Week 12 visit.

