As site is included in the primary ANCOVA model, a treatment-by-site interaction will be investigated as an exploratory analysis to assess the homogeneity of treatment effects across site. This effect will be investigated analytically prior to any pooling of sites by adding the interaction term to the ANCOVA model and testing for significance. Because interactions are not powered in this study, testing for significance will be at the 0.10 level. However, any significant interaction findings at the 0.10 level will also take into account the potential for spurious results. Further exploration may be done graphically with interaction plots to determine the nature of the interaction and to identify any “outlier” sites with attention focused on qualitative differences in treatment effects. If large differences in treatment effects are seen in any “extreme” sites, then sensitivity analyses will be performed that exclude sites with the highest extreme treatment effect values from the analysis. Any such sites may be further investigated for explanation involving study conduct, subject demographics, current medications, etc.

In addition, the following sensitivity analyses will be performed:

- Inflammatory lesion count data will be analyzed for CFB at Week 12 according to an ANCOVA model with the baseline value as a covariate and effects of treatment and (pooled) site using the PP population with OC data.

- LOCF will be used as an imputation method for cases where the Week 12 CFB in inflammatory lesion counts value is missing. The endpoint will then be analyzed according to an ANCOVA model with the baseline value as a covariate and effects of treatment and (pooled) site.
- Baseline observation carried forward will be used as an imputation method for cases where the Week 12 CFB in inflammatory lesion counts value is missing. The endpoint will then be analyzed according to an ANCOVA model with the baseline value as a covariate and effects of treatment and (pooled) site.

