10.1.2 IGA Success

The co-primary efficacy endpoint, percentage of subjects with IGA success at Week 12, will be analyzed for the ITT population using the CMH test with adjustment for (pooled) site. Missing data will be imputed using an MI approach further described in Section 16.2. The rate difference and the 95% CIs for the rate difference and the relative rate and the 95% CIs for the relative rate will be presented as well. The CI for the treatment rate difference will be based on two-sided 95% Wald type CIs with CMH weights (Kim & Won, 2013, Yan & Su, 2010).

The homogeneity of treatment effects across (pooled) site will be investigated as an exploratory analysis using the Breslow-Day test. If the Breslow-Day test indicates large heterogeneity in the odds ratios across (pooled) site, then further exploration may be done graphically or with further investigation for explanation involving study conduct, subject demographics, current medications, etc.

In addition, the following sensitivity analyses will be performed:

- IGA success at Week 12 will be analyzed using a CMH test with adjustment for (pooled) site on the PP population with OC data.
- For IGA success, subjects who discontinue from the study early will be coded as failures for the Week 12 analysis. A sensitivity analysis of IGA success using this data handling convention will be performed using a CMH test with adjustment for (pooled) site.
- For IGA success, subjects who discontinue from the study early will be coded as failures for subjects on sarecycline and successes for subjects on placebo. A sensitivity analysis of IGA success using this data handling convention will be performed using a CMH test with adjustment for (pooled) site.

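### The worst-case IGA sensitivity analysis recodes by early discontinuation, not by a missing Week 12 IGA, so it overwrites observed scores of late discontinuers

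*SAP*

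**What the plan says.** Protocol 11.5.6 gives the purpose of the sensitivity analyses of the co-primary endpoints: "to explore the impact of missing data on the robustness of the results".

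For lesion counts, the trigger is a missing value. SAP 10.1.1 states that "LOCF will be used as an imputation method for cases where the Week 12 CFB in inflammatory lesion counts value is missing", and the baseline-carried-forward bullet has the same condition.

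For IGA success, SAP 10.1.2 has two recoding analyses, both triggered by leaving the study:
- All-failure (second bullet): "subjects who discontinue from the study early will be coded as failures for the Week 12 analysis".
- Worst case (third bullet): "subjects who discontinue from the study early will be coded as failures for subjects on sarecycline and successes for subjects on placebo".

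The categorical bullets of Protocol 11.5.6 use the same trigger and name the ITT population. Neither document adds the condition that the Week 12 IGA be missing.

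Two other rules matter. Protocol 9.5.2.7 asks for the Visit 4 assessments, which include the facial IGA, at early termination where possible. SAP 16.1 assigns every assessment from Day 75 onward to Week 12, with no upper limit.

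**The concern.** Discontinuing early and lacking a Week 12 IGA are different conditions under this plan. A subject who stops late and has an early-termination IGA on Day 75 or later has both a discontinuation record and an observed Week 12 score. The primary analysis uses that score. The worst-case analysis replaces it with the value least favourable to sarecycline: an observed placebo failure becomes a success, and an observed sarecycline success becomes a failure. That contradicts data in hand and is not an assumption about missing data.

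Interpretation is what is at stake. If the worst case disagrees with the primary result, a reader cannot tell how much comes from unknown outcomes and how much from known outcomes that were overwritten. The two co-primary endpoints are also stressed on different sets of subjects.

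A smaller gap lies on the other side. A subject who completes but has no Week 12 IGA has a missing score, and neither IGA bullet says what happens to it.

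**Working it through.** **Who is affected, from the text**

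| Subject | Week 12 IGA under SAP 16.1 | Worst-case rule as written |
|---|---|---|
| Discontinues, last IGA before Day 75 | Missing | Recoded, as intended |
| Discontinues, IGA on Day 75 or later | Observed, used in primary analysis | Overwritten |
| Completes, IGA present | Observed | Kept |
| Completes, no Week 12 IGA | Missing | No stated rule |

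**The plan's own figure.** SAP 14.0 assumes 23% v 10%, two-sided 0.05 and 90% power, and states 170 per arm. With the pooled chi-square formula and mean rate 0.165:

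n = [1.960·√(2·0.165·0.835) + 1.2816·√(0.23·0.77 + 0.10·0.90)]² / 0.13² = (1.029 + 0.662)² / 0.0169 ≈ 169.2, so 170. This reproduces.

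**Size of the effect.** Inputs from the documents are 23%, 10% and 500 per arm (SAP 14.0). The following are assumptions, because the documents do not give them: D, the share discontinuing in each arm; s, the share of those with an IGA on Day 75 or later; no completer missing; and the planned rates among everyone not recoded.

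If a share r of each arm is recoded to the worst case:
- sarecycline = 0.23(1 − r)
- placebo = 0.10(1 − r) + r
- difference = 0.13 − 1.13r

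As written, r = D. Keyed to missing scores, r = D(1 − s). The gap between the two rules is 1.13·D·s.

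For D = 10% (50 per arm), with a pooled two-proportion z:

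| s | Observed scores overwritten per arm | As written | Keyed to missing |
|---|---|---|---|
| 0% | 0 | 1.7 points (z 0.67) | 1.7 points (z 0.67) |
| 10% | 5 | 1.7 points (z 0.67) | 2.8 points (z 1.13) |
| 25% | 12.5 | 1.7 points (z 0.67) | 4.5 points (z 1.82) |
| 50% | 25 | 1.7 points (z 0.67) | 7.4 points (z 3.01) |

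Check by counting at s = 25%: of 12.5 overwritten placebo subjects, 0.90 × 12.5 = 11.25 were failures and become successes. Of 12.5 overwritten sarecycline subjects, 0.23 × 12.5 = 2.875 were successes and become failures. (11.25 + 2.875) / 500 = 2.8 points, the gap in the table.

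**All-failure analysis.** The difference is 0.13(1 − r). With D = 10% and s = 25% it is 11.7 points as written and 12.0 keyed to missing, so the trigger hardly matters there.

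**Completers without a Week 12 IGA.** With D = 10%, s = 0 and 3% of completers missing (0.03 × 450 = 13.5 per arm), leaving those scores at the planned rates gives 1.7 points. Including them in the worst case gives r = 0.127 and 0.13 − 1.13·0.127 = −1.4 points. This gap runs in the opposite direction.

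**The case against.** The strongest reply is that little turns on this. The analysis is supportive and outside the testing hierarchy. Overwriting can only make the worst case harsher on sarecycline, so overwriting alone cannot create a false impression of robustness. The share of late discontinuers may also be small: if discontinuation were uniform over 85 days, Days 75 to 81 (before the Visit 4 window opens) would be 7/85 = 8% and Days 75 to 85 would be 11/85 = 13%. At D = 10% the keyed difference would then be 2.6 to 3.2 points, against 1.7. All of this stands and limits the severity. It does not remove the mismatch between the stated purpose and the trigger.

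It is also fair to say that the all-failure bullet can be read as a composite analysis in which leaving early counts as failure. That is a legitimate choice if labelled so.

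Several stronger readings are tempting but not supported:
- *That missing scores go untouched.* Subjects who leave before Day 75, normally the main source of missing data, are recoded.
- *That completers without a Week 12 IGA are dropped.* No rule is stated. The protocol names the ITT population, SAP 10.1.2 uses multiple imputation in the primary analysis, and Protocol 9.3.4 ("Withdrawn subjects are those who do not complete all evaluations and procedures outlined in the protocol") could even be read to class them as withdrawn.
- *That PK Schedule 3 children are misclassified.* Their termination form moves to Visit 5, so a child with full Week 12 data who misses that visit might count as a non-completer, also under the SAP 6.4 wording "did not complete study based on subject exit status". But Visit 5 is described as follow-up, SAP 7.0 counts discontinuation from the treatment period, and the per-protocol list is reviewed before unblinding. This is an ambiguity in a small group.
- *That these are the only ITT sensitivity analyses of IGA.* SAP 10.6 is redacted, so this cannot be established.

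**Conclusion.** The point holds for the worst-case bullet. As written, it replaces observed Week 12 IGA scores of late discontinuers with contrary values, although the analysis is meant to address missing data. At 10% discontinuation the worst-case difference is understated by about 1.1 points if 10% of discontinuers are seen from Day 75, and by about 2.8 points if 25% are. The two rules coincide if no discontinuer is seen from Day 75 and no completer is missing.

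A reader might infer that the sign or nominal significance of the worst case hinges on the trigger. Inputs can be found that do this: at D = 15% and s = 25% the difference is −4.0 points as written and +0.3 keyed to missing. But the documents give neither share, so such reversals illustrate the arithmetic and are not findings about this trial. The net direction could also change if completers' missing scores are left out of the worst case.

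Severity is minor. The primary analysis, the testing hierarchy and the sample size are unaffected.

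**What to change.** - **Worst-case bullet** (SAP 10.1.2, third bullet, and its counterpart in Protocol 11.5.6): apply the recoding to ITT subjects whose Week 12 IGA is missing after the SAP 16.1 windows are applied, and keep every observed Week 12 score. This also gives completers with a missing score a rule.
- **All-failure bullet:** use the same trigger, or keep the present one and label the analysis as a composite in which discontinuation counts as failure.
- **PK Schedule 3:** state that completion for efficacy purposes, including the SAP 6.4 exit-status criterion, is judged at Visit 4.

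The cost is a few sentences and one changed flag in the programs, with no new data. The downside is that the worst-case analysis no longer treats late discontinuation itself as an outcome. If that is wanted, it can be kept as a separately labelled analysis.

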10.2 SECONDARY EFFICACY PARAMETERS

There will be 8 sets of secondary efficacy endpoints for this study: percent CFB in inflammatory lesion counts at Week 12, absolute and percent CFB in inflammatory lesion counts at Weeks 9, 6, and 3, and absolute and percent CFB in noninflammatory lesion counts at Weeks 12, 9, 6, and 3. These variables will be considered continuous variables.

A hierarchical testing approach will be used for the secondary efficacy endpoints, such that statistical testing will only be performed if both co-primary efficacy endpoints are statistically superior to placebo at $\alpha=0.05$. In addition, statistical testing of the secondary endpoints will be conducted in the following order, with all tests proceeding at the 0.05 level if and only if the previous tests were all significant at the 0.05 level:

1. Percent CFB for inflammatory lesion counts at Week 12
2. Absolute and percent CFB for inflammatory lesion counts at Week 9 (both endpoints must be significant at the 0.05 level to proceed to the next analyses)
3. Absolute and percent CFB for inflammatory lesion counts at Week 6 (both endpoints must be significant at the 0.05 level to proceed to the next analyses)
4. Absolute and percent CFB for inflammatory lesion counts at Week 3 (both endpoints must meet the 0.05 level for Week 3 to meet statistical significance)
5. Absolute and percent CFB for noninflammatory lesion counts at Week 12 (both endpoints must be significant at the 0.05 level to proceed to the next analyses)
6. Absolute and percent CFB for noninflammatory lesion counts at Week 9 (both endpoints must be significant at the 0.05 level to proceed to the next analyses)
7. Absolute and percent CFB for noninflammatory lesion counts at Week 6 (both endpoints must be significant at the 0.05 level to proceed to the next analyses)

8. Absolute and percent CFB for noninflammatory lesion counts at Week 3 (both endpoints must meet the 0.05 level for Week 3 to meet statistical significance)

These endpoints will be analyzed for each visit using an analysis of covariance (ANCOVA) model with terms included to represent effects of treatment and (pooled) site and the baseline values as a covariate for the ITT population. Missing data will be imputed using an MI approach, as described in Appendix 16.2. The adjusted means with associated 95% CIs for the ANCOVA model will also be presented for each treatment and for the difference between the treatments. Statistical significance between the treatments, sarecycline compared to placebo, will be declared if the p-value of the hypothesis test from the ANCOVA model is less than or equal to 0.05.

For the Week 12 percent CFB analysis, as site is included in the ANCOVA model, a treatment-by-site interaction will be investigated as an exploratory analysis to assess the homogeneity of treatment effects across site. This effect will be investigated analytically by adding the interaction term to the ANCOVA model and testing for significance. Because interactions are not powered in this study, testing for significance will be at the 0.10 level. However, any significant interaction findings at the 0.10 level will also take into account the potential for spurious results with attention focused on qualitative differences in treatment effects. If large differences in treatment effects are seen in any “extreme” sites, then sensitivity analyses will be performed that exclude sites with the highest extreme treatment effect values from the analysis. Further exploration may be done graphically with interaction plots to determine the nature of the interaction and to identify any “outlier” sites. Any such sites may be further investigated for explanation involving study conduct, subject demographics, current medications, etc.

An additional exploratory analysis will be done for the percent CFB analysis by visit. A rank transformation will be applied to each of the multiple datasets created from the MI approach and the analysis will proceed using an ANCOVA model on the ranks with the baseline value as a covariate and effects of treatment and (pooled) site. Tied values will receive the mean value (midranks) of the corresponding ranks.

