11.5.3 Secondary Endpoint Analyses

A hierarchical testing approach will be used for the secondary efficacy endpoints, percent CFB in inflammatory lesion counts at Week 12, **and absolute and percent CFB in inflammatory lesion counts at Weeks 9, 6, and 3 (using ANCOVA), such that statistical testing will only be performed if both co-primary efficacy endpoints are statistically superior to placebo at $\alpha=0.05$.** **In addition, statistical testing of the secondary endpoints will be conducted in the following order, with all tests proceeding at the 0.05 level if and only if the previous tests were all significant at the 0.05 level:**

- 1. Percent CFB for inflammatory lesion counts at Week 12 (must be significant at the 0.05 level to proceed to the next analyses)**
- 2. Absolute and percent CFB for inflammatory lesion counts at Week 9 (both endpoints must be significant at the 0.05 level to proceed to the next analyses)**
- 3. Absolute and percent CFB for inflammatory lesion counts at Week 6 (both endpoints must be significant at the 0.05 level to proceed to the next analyses)**
- 4. Absolute and percent CFB for inflammatory lesion counts at Week 3 (both endpoints must meet the 0.05 level for Week 3 to meet statistical significance)**

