10.0 EFFICACY ANALYSES

The efficacy analyses will be based on the ITT Population. All summaries on this population will be based on the investigational product each subject was randomized to receive. The multiple imputation (MI) approach will be used to impute missing values for co-primary and secondary efficacy analyses and details are further described in Section 16.2. Sensitivity analyses for efficacy parameters will be performed using alternative approaches to handle missing data, as well as an observed cases (OC) approach using the PP population. *Baseline* for efficacy is defined as the last non-missing efficacy assessment before the first dose of the investigational product. All statistical tests will be 2-sided hypothesis tests performed at the 5% level of significance for main effects. All confidence intervals will be 2-sided 95% confidence intervals, unless stated otherwise.

The descriptive statistics for all the continuous variables will include the mean, median, 25th percentile, 75th percentile, standard deviation (SD), standard error of mean (SEM), minimum, maximum, and number of subjects. Descriptive summaries will be provided for raw, change from baseline (CFB), and %CFB values for continuous efficacy endpoints. Frequency distributions for all the categorical variables will be presented as counts and percentages. Summaries will be provided by visit and treatment, as appropriate.

While every effort will be made to randomize a sufficient number of subjects at each study site, in the event that this is not possible, study sites may be pooled for statistical inference testing. Study sites (centers) will be pooled by geographical location based on region definitions from the US Census Bureau (Northeast, Midwest, South, and West; US Census Bureau, 2013) for analysis purposes so that in each pooled site the number of subjects is reasonably large and consistent in size between pooled sites. Sites within a geographic location will be pooled starting with the sites that have the lowest number of randomized subjects pooled together such that the pooled site has a minimum of 12 randomized subjects after pooling.

The sites to be pooled for each geographic location will be documented in a signed memo prior to unblinding of the treatment code. A list of sites and the corresponding pooled sites will be presented.

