16.9 CHARACTER VALUES OF CLINICAL LABORATORY PARAMETERS

If the reported value of a clinical laboratory parameter cannot be used in a statistical summary table because, for example, a character string is reported for a parameter of the numeric type, a coded value must be appropriately determined for use in the statistical analyses. The actual values, however, as reported in the database will be presented in the data listings.

Table 16.9–1 shows examples of how some possible laboratory results should be coded for the analysis.

Table 16.9–1. Examples of Coding Special Character Values for Clinical Laboratory Parameters

Laboratory Test, SI Unit	Possible Laboratory Results	Coded Value for Analysis
CHEMISTRY		
ALT, U/L	< 5	0
AST, U/L	< 5	0
Bilirubin, total, $\mu\text{mol/L}$	< 2	0
URINALYSIS		
Glucose, mmol/L	= OR $> 55, \geq 55, > 0$	Positive
	≤ 0 , negative	Negative
pH	$> 8.0, \geq 8.0$	8.0
	≥ 8.5	8.5
Protein	= OR $> 3.0, \geq 3.0, > 0$	Positive
	≤ 0	Negative

ALT = alanine aminotransferase; AST = aspartate aminotransferase; SI = *Le Système International d'Unités* (International System of Units).

17.0**CHANGES IN AMENDMENT 1 OF THE STATISTICAL ANALYSIS PLAN**

Rationale: This SAP, Amendment 1 is being updated prior to database lock to allow for the non-inflammatory lesion count assessment to be considered as a secondary efficacy endpoint. It will be included in the hierarchy of testing of the secondary endpoints to maintain type 1 error control at 0.05. Since this change is occurring after the completion of all patients in the study, and given that there is no impact on patient safety or study conduct, the protocol will not be amended to reflect this change.

Summary of changes: Sections 10.2, 11.5.1, and 16.2 have been updated to add non-inflammatory lesion count changes from baseline as a secondary efficacy endpoint and to reflect the dual nature of this parameter as being evaluated both for efficacy and for safety.

18.0

REFERENCES

Littell, R. C., Milliken, G. A., Stroup, W. W., Wolfinger, R. D., and Schabenberger, O. (2006), *SAS for Mixed Models*, Second Edition, Cary, NC: SAS Press.

Rubin, DB. Inference and missing data. *Biometrika*. 1976;63:581-592.

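### SAP 10.2 has two rules for paired secondary tests, and in steps 2, 3, 5, 6 and 7 the text does not secure the 0.05 type 1 error control that SAP 17.0 claims

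*SAP*

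**What the plan says.** SAP 10.2 tests the secondary endpoints in eight steps once both co-primaries have succeeded, "with all tests proceeding at the 0.05 level if and only if the previous tests were all significant at the 0.05 level". Step 1 is a single test. Steps 2 to 8 each hold two tests, absolute and percent change from baseline (CFB) at one visit.

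The condition on the pair comes in two forms:

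- **Steps 4 and 8** (Week 3, inflammatory and noninflammatory): "both endpoints must meet the 0.05 level for Week 3 to meet statistical significance". This is a condition for declaring a result.
- **Steps 2, 3, 5, 6 and 7**: both must be significant in order to continue. Step 5 reads "noninflammatory lesion counts at Week 12 (both endpoints must be significant at the 0.05 level to proceed to the next analyses". This is a condition for moving on.

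The text after the list says that significance "will be declared if the p-value of the hypothesis test from the ANCOVA model is less than or equal to 0.05". It does not mention the paired endpoint. No alpha split, Holm or Hochberg step, or order within a pair is given.

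On the noninflammatory endpoints that Amendment 1 added, SAP 17.0 says: "It will be included in the hierarchy of testing of the secondary endpoints to maintain type 1 error control at 0.05".

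Protocol 11.5.3 uses the same two forms in its shorter, four-step list, for example "Absolute and percent CFB for inflammatory lesion counts at Week 9 (both endpoints must be significant at the 0.05 level to proceed to the next" for Week 9.

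**The concern.** A fixed sequence controls error between steps. Within a step that holds two unordered tests, control needs a further rule: both must succeed, or one comes first, or alpha is divided. Steps 4 and 8 state such a rule. In the other five paired steps the text says what a split result does to the next step, but not whether the one significant endpoint may be claimed.

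Take noninflammatory Week 12 with absolute p = 0.03 and percent p = 0.08. Under the step 4 and 8 wording nothing is claimed. Under step 5 plus the declaration sentence, testing stops but the absolute change could be reported as a controlled finding. Step 5 opens the block that was added so that these endpoints could carry type-1-controlled claims, after all patients had completed the study. The answer should not be left to interpretation after unblinding.

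**Working it through.** **Inputs from the documents**

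- Each test is two-sided at 0.05 (SAP 10.0: "All statistical tests will be 2-sided hypothesis tests performed at the 5% level of significance for main effects"), so the critical value is 1.96.
- Entry limits (Protocol 9.3.1, IN04): 20 to 50 inflammatory lesions; up to 100 noninflammatory lesions with no minimum.
- Stated control of the hierarchy: 0.05 (SAP 17.0).

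**Assumption.** The correlation r between the absolute and percent CFB test statistics is not in the documents, so a range is shown.

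**Step 1: the stated figure.** With a single test, or a pair under a both-required rule, error at a step is at most 0.05, so the SAP 17.0 figure is reproduced. It is not reproduced if either endpoint may be claimed.

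**Step 2: the literal rule at one paired step.** Suppose the earlier steps are passed and neither endpoint of the pair has a true effect. Then

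P(at least one false claim) = 1 − P(|Z1| ≤ 1.96 and |Z2| ≤ 1.96),

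with (Z1, Z2) standard bivariate normal with correlation r. At r = 0 this is 1 − 0.95² = 0.0975. For any dependence it cannot exceed 0.05 + 0.05 = 0.10. The chance that both are significant is 0.10 minus the first figure.

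| r | Either may be claimed | Both required |
|---|---|---|
| 0 | 0.0975 | 0.0025 |
| 0.4 | 0.093 | 0.007 |
| 0.5 | 0.091 | 0.009 |
| 0.7 | 0.084 | 0.017 |
| 0.8 | 0.078 | 0.022 |
| 0.9 | 0.070 | 0.030 |
| 0.94 | 0.066 | 0.034 |
| 0.95 | 0.065 | 0.035 |
| 0.97 | 0.061 | 0.039 |
| 1 | 0.050 | 0.050 |

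The both-required column assumes no effect on either endpoint. If one effect is certain and the other is null, that rule gives 0.05, which is its maximum.

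**Step 3: plausible correlations.** Percent CFB is absolute CFB divided by baseline, so r depends on how widely baseline varies. I took baseline uniform within the entry limits, adjusted both measures for baseline, and tried an error SD that was either constant or proportional to baseline.

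- *Inflammatory, baseline 20 to 50:* r is about 0.96 to 0.97, so the error is about 0.06.
- *Noninflammatory, upper limit 100, assumed minimum 1, 5, 10 or 20:* r is 0.41, 0.69, 0.80 or 0.90 with constant SD, and 0.87, 0.88, 0.90 or 0.93 with proportional SD. Simulated null trials with an ANCOVA on baseline gave r up to 0.94. Over 0.4 to 0.94 the error runs from about 0.093 down to 0.066.

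**Step 4: the whole hierarchy.** Suppose nothing is effective from some paired step onward. Going past that step needs both of its tests to be significant, and that is already a false claim. Later steps therefore add no new way to make a first error. The familywise error equals the figure for the first null pair: simulation of the literal rule starting at step 5 gave 0.097, 0.078 and 0.064 at r = 0, 0.8 and 0.95.

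**Step 5: the remedies.** The both-required rule gives at most 0.05. A fixed order within the pair gives 0.05, because the second endpoint is tested only after the first has been declared.

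**The case against.** The strongest reply is that the sponsor meant a joint rule throughout and only the wording varies. Four points support it.

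1. Nothing in either document expressly lets one endpoint of a pair be claimed alone.
2. The counting treats a pair as a unit. Protocol 11.4.2 lists 1 + 2 × 3 = 7 variables but counts four secondary endpoints. SAP 10.2 lists 1 + 2 × 3 + 2 × 4 = 15 variables in eight sets, one per step.
3. In Protocol 11.5.3, Week 3 is the last step. There is nothing to proceed to, so the same rule had to be phrased differently.
4. The declaration sentence is general: SAP 10.1.1 uses it for the lesion-count co-primary too. Read as free-standing, it would override the whole hierarchy.

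The first two points stand: a joint reading is available, and under it control at 0.05 holds. The third explains the protocol but not the SAP, where step 4 is followed by step 5 and yet keeps the declaration rule, while the newly added step 5 carries only the rule for continuing. The fourth shows that the sentence must be read subject to the hierarchy, but for steps 2, 3, 5, 6 and 7 the hierarchy supplies no rule on claims to which it could be subject.

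A reader might go further and infer that the procedure definitely fails to control error at 0.05. The documents do not support that, because the failure depends on taking the permissive reading.

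**Conclusion.** The point holds as a gap in the decision rule. As written, SAP 10.2 does not secure the 0.05 control stated in SAP 17.0 for steps 2, 3, 5, 6 and 7; whether control is lost depends on how a split result is treated.

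Under the permissive reading, the error at the first null pair is about 0.06 for the inflammatory steps 2 and 3, a small excess. For the noninflammatory steps 5 to 7 it is about 0.066 to 0.09, or roughly 1.3 to 1.9 times 0.05 at the two ends of the assumed correlation range (0.066/0.05 = 1.3; 0.093/0.05 = 1.9). The upper end needs a constant error SD and baselines close to zero. These figures rest on assumed correlations and baseline distributions; 0.0975 is the ceiling for any non-negative correlation. Counting only errors in favour of sarecycline, 0.025 becomes at most 0.0494.

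Two limits apply. A reader might infer that five loose steps multiply the excess, but they do not, because continuing requires both endpoints of the pair. Exposure is also conditional: step 5 is reached only after both co-primaries and seven secondary tests are significant. The co-primaries, step 1 and steps 4 and 8 are unaffected.

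**What to change.** Before unblinding, put one rule in SAP 10.2 for all paired steps: significance at a given week is declared only if absolute and percent CFB both have p ≤ 0.05; otherwise neither is declared and testing stops. Make the declaration sentence after the list expressly subject to that rule.

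Alternatively, fix an order within each pair, for example absolute first and percent only if absolute is significant. Either option gives control at 0.05.

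The cost is a sentence or two of SAP text, with no new data and no change in sample size. Under the joint rule a split result supports no claim. Under the ordered rule it supports a claim only for the endpoint placed first, and only if that is the significant one.
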